3 HUMAN SUBJECTS PROTECTION

3.1 RECRUITMENT AND INFORMED CONSENT

Quantitative Study: After obtaining Alaska Area Institutional Review Board (IRB) and appropriate Tribal review and clearance, a list of eligible patients will be drawn from each participating THOs electronic medical record (EMR) system. Each healthcare system in the ATHS uses comprehensive EMRs and administrative databases that will be used to collect contact information (e.g., phone number(s) and mailing address), demographic information (e.g., age, sex, and race and ethnicity), identify patients due for screening, provider orders, screening test completion, and pathology results. Prior history of CRC screening, including time since the last screening, will be retrospectively collected from EMRs. Current Procedural Terminology, Healthcare Common Procedure Coding System, and laboratory codes will be used to ascertain receipt of screening and screening method, regardless of indication. See Appendix A for list of variables to be collected. All variable data collected for this study will be stored in REDCap (Research Electronic Data Capture), a secure HIPAA compliant database system.

Communities will be randomized to one of two interventions: high intensity or medium intensity. The high intensity intervention will include navigated outreach, a mailed MT-sDNA kit, mailed culturally appropriate educational material describing CRC screening options available, and follow-up reminders (Study Group 1). The medium intensity intervention will include mailed culturally appropriate educational material describing CRC screening options available, including MT-sDNA, and navigated follow-up outreach reminders (Study Group 2). Participants will be recruited by mail and phone calls, depending on the intervention arm. All remaining communities in the region served by that THO will receive usual care and will not have direct outreach.

Patients who requested MT-sDNA for CRC screening, received a kit, but did not return it will be contacted to assess reasons for non-adherence. Survey data will be collected verbally by phone by an ANTHC study team member and stored in REDCap, a secure HIPAA compliant database system. This data will be stored with identifying information such as name and phone number, which is needed to contact patients for the phone survey but no personally identifying information will be included in the reporting of the non-adherence data analysis.

Waiver of Consent: As individuals will be selected for each trial arm based on their randomized community, we requested a waiver of informed consent for eligibility and group assignment from the Alaska Area IRB as well as the Alaska Native Tribal Health Consortium (ANTHC) and the ANTHC and SCF Privacy Officers, who have given approval for the waiver of consent. We will also request a waiver of informed consent from participating THOs prior to study implementation.

The rationale for the waiver of consent is that the study will randomize by community (cluster randomization) so that everyone who is eligible for CRC screening in that community will be offered the same intervention (or usual care). The disclosure of the study purpose as part of the consent process to individuals would bias the research so that the results will not be meaningful, since the study is trying to determine on a community level how much offering these different types of CRC screening interventions would help increase overall community screening rates. The purpose of the waiver of informed consent is to avoid potential selection/volunteer bias. Additionally, if participants are consented, they will know which intervention community they are in, and so there might be bias resulting from that as well. Patients who did not return their mt-sDNA kit for CRC screening and those that scheduled a colonoscopy but never completed it will be contacted for a phone survey and fall under this waiver of consent. These are patients who participated in the intervention and are being followed up with to assess why they chose to screen with mt-sDNA or colonoscopy, but ultimately did not return their kit or complete a procedure to complete screening.

To help address potential concerns raised by this type of study design, the regional THOs and their Privacy Officers will be asked to approve the waiver of consent prior to study implementation. Clinic staff (front desk, Community Health Aides, midlevel providers) in intervention communities will be

informed that a CRC outreach project is occurring in case they are contacted by community members but not which arm their community is in. Lastly, since the risks posed by this intervention do not exceed the threshold of minimal risk, an independent monitoring committee (Data and Safety Monitoring Committee; DSMC) is not required. However, to provide additional safeguards for this study, we will engage a DSMC to provide study oversight and consultation (see 3.3.2. *Data and Safety Monitoring Plan*).

Qualitative Study: We will recruit never or inadequately screened patients and Alaska tribal health system providers to participate in either focus groups (patients only) or key informant interviews (patients and providers) to identify barriers to receipt of CRC screening, as well as explore opportunities to increase screening using the MT-sDNA test. We will recruit Alaska Native patients who have not been screened or are not currently adherent to screening recommendations (colonoscopy within 10 years, sigmoidoscopy within five years, or FIT/FOBT within preceding 12 months) according to their tribal medical records at ANMC and at 1-2 participating regional THOs. Clinical staff will be recruited based on their involvement in the provision of CRC screening at the participating organizations.

Recruitment for focus groups will be conducted by Hays Research Group LLC to increase our chance of successfully recruiting the required number of AN people to participate in the focus groups. Hays Research Group LLC has extensive experience recruiting for and conducting health-related focus groups with AN people and has previously conducted focus groups for the EpiCenter and others within the ATHS. We will also use IRB- and tribally-approved study flyers and information sheets located at the Alaska Native Medical Center in Anchorage, AK and participating rural THOs to recruit for the study.

Upon recruitment, we will explain the purpose of the qualitative study to participants, and thoroughly review the consent with each participant individually (including for focus group participants). All focus group participants and key informants will sign an informed consent form that describes the focus group/interview, how the information that they provide will be used, and how their confidentiality will be protected. No names of participants will be associated with notes or transcriptions. We will have a translator available for those participants who have difficulty with the consent forms, or who would like further clarification in their Native language. Per Alaska Area IRB requirements, all consent forms and study documents will be written at grade 8 reading level or lower. All documents will be reviewed and approved by the IRB and necessary THOs.

There will be a short, anonymous questionnaire distributed before the focus group or interview to collect some general demographic information about the participants (age, gender, community). Focus groups will last approximately 2 hours and will be stratified by gender. Interviews are expected to take approximately 30-45 minutes of staff time. Focus groups may be completed using the Zoom platform which is a HIPAA compliant web and video conferencing platform. In this case, focus groups will still be recorded so they can be transcribed and participant names will be excluded from the transcripts. Focus group guides have been created for both in-person and virtual focus groups and the appropriate guide will be utilized depending on the method we use. The focus groups and interviews will be tape-recorded and the tapes transcribed by a private transcription service (temi.com) to ensure no voice recognition by the transcriber. The analysis, interpretation, and reporting will be done by EpiCenter staff trained in research and with current CITI certifications on file with the AAIRB. Qualitative computer software (ATLAS.ti) may be used for analysis as needed.

Focus group and interview participants will be given a thank you gift for their time. This will be a gift card, at a value to be determined in collaboration with our THO partners, and after approval from the Alaska Area IRB. In addition to gift certificates for focus group participants we will have \$25 taxi cab and \$25 childcare vouchers to help people be more readily able to participate in the focus groups. These will be offered to all in-person focus group participants in THO regions where we conduct in-person

focus groups. Our previous studies have provided \$25 for interviews and \$50 for focus group participation. We do not anticipate the need for additional retention strategies, as interviews and focus groups will be one-time, and will occur soon after recruitment (ideally <7 days).

3.2 POTENTIAL RISKS

We will collect information on CRC screening clinical care including in tribal electronic medical record (EMR), as well as data from the Alaska Native Tumor Registry (ANTR). There is a small risk of loss or accidental release of personally identifiable information during data extraction. Risk associated with this occurrence is expected to be minimal, as personally identifiable information will not be included in the study database. The research team will have access to personally identifiable information only for the purpose of medical chart review. The Alaska Native Health Campus is a Covered Entity; all electronic data will be stored in the secure, password-protected campus network system and only the study research team designated in the Alaska Area IRB-approved protocol have access to the data. Any paper recorded (e.g., informed consent documentation) will be stored in locked cabinets in the Alaska Native Epidemiology Center office. Access to this area is restricted to keycard holders only; only the PI and Study Coordinator will have direct access to this key.

It is possible that there may be the potential for stigmatization of or concern from the Alaska Native community regarding findings from the analyses. We believe the risk of this to be small, due to collaboration with and oversight by tribal review entities (see below).

As with all scientific studies, it is possible that we will not generate results that will have direct therapeutic or preventive benefit to Alaska Native people. This possibility is not likely to cause adverse effects.

3.3 PROTECTION AGAINST RISK

Every effort will be made to maintain the confidentiality of the participants' personal information. Files and computers are accessible only to the Study's research team. Care will be taken to ensure that information is collected and presented in such a way that individuals cannot be identified. For example, no personally identifiable information will be included in the study database used for analysis. The research team will have access to personally identifiable information only for the purpose of medical chart review to determine CRC screening completion and outcomes.

All research team members have been trained in HIPAA, confidentiality and medical record compliance standards, as appropriate. Furthermore, all ANTHC research staff sign a Confidentiality Statement as a condition of employment, which is reviewed annually and includes a clause indicating a break in confidentiality is grounds for immediate dismissal. All members of the research team have verification of Collaborative Institutional Training Initiative (CITI) human subject protections training. All investigators and staff members involved in the project will sign confidentiality and data use agreements to avoid misuse or accidental release of data. Access to research data will be strictly limited to study staff directly involved in data analysis and interpretation, under the direction of the PI and Study Coordinator.

Access to research data will be strictly limited to study staff directly involved in data analysis and interpretation, under the direction of the PI. Study staff will only be given access to the minimum necessary information to complete their assigned tasks. For example, the Research Assistant will have access to limited personally identifiable information for a limited period of time, in order to complete medical chart review as described above. Any data that is shared with investigators external to ANTHC will be shared only with completion of a signed ANTHC Data Use Agreement. Only aggregated, de-identified data will be shared with other consultants, and any other individuals who may assist in the data interpretation process (e.g., tribal health leaders, ANTHC Research Consultation Committee).

We will work closely with ANTHC and regional tribal researchers and review boards to ensure that all

results are presented in a culturally appropriate, respectful way. All dissemination materials will present data in aggregate or summary form and in no way will identify individual participants. This protocol, and all materials designed to disseminate information or results from this study, will undergo ANTHC and regional THO tribal review and clearance.

3.3.1. Storage and Coding of Data

ANTHC data files are managed, processed, and stored in a secure environment (e.g., lockable computer systems with passwords, firewall system in place, virus/malicious intruder protection) and by controlling access to digital files with encryption and/or password protection. Necessary data security and storage mechanisms will be used as required by applicable laws to protect personal health information as per ANTHC policy. Login permissions to the shared folder are managed by ANTHC IT Administrators or the designated Data Manager. The Data Manager will also be responsible for naming conventions, version control, folder structures, and data dictionaries (as needed). The Data Manager will assign each individual in the linked database with a unique study ID that will be associated with the participant's information. The study PI will be responsible for ensuring that all data are kept secure and that the data management plan is reviewed annually.

3.3.2. Data and Safety Monitoring Plan

This is no more than a minimum risk study with a CRC screening intervention. Because the risks posed by this intervention do not exceed the threshold of minimal risk, an independent monitoring committee (Data Safety Monitoring Committee; DSMC) is not required. However, to provide additional safeguards for this study with AN people, we will engage a DSMC to provide study oversight and consultation. The DSMC for this clinical trial will consist of three (3) experts who are independent of this protocol. [name], Director of Wellness & Prevention at ANTHC will be asked to chair the DSMC. The other DSMC members who will be invited to participate will include [name], Director of Research and Clinical Services at ANTHC, and [name], clinical gastroenterologist at the Alaska Native Medical Center. [name] oversees ANTHC's Research Department and is the PI for a clinical intervention trial currently underway at ANTHC. [name] is a clinical gastroenterologist at the Alaska Native Medical Center. A representative of the participating regional THOs will be invited to join the committee if they would like to be involved.

The DSMC will review data on such aspects as participant enrollment, site visits, study procedures, data quality, and other measures of adherence to protocol. The DSMC will review data and individual reports related to unanticipated problems and adverse (AEs) and serious adverse events (SAEs). They will provide recommendations to the PI regarding problems and safety concerns. They will provide periodic reports to the PI indicating whether they see any reasons for change and document all their actions. The data manager will prepare tables with data to be reviewed by the DSMC at least annually.

All reportable AE, SAE and unanticipated problems experienced by participants will be reported to the AAIRB in addition to any adverse or serious adverse events in compliance with their Adverse Event Reporting Policy requirements. Within 72 hours after a reportable AE, SAE or unanticipated problem has been reported by the participant, it will be graded by the PI, forwarded to the study's DSMC for review, and then will be submitted by the PI to the AAIRB. In addition, all cumulative reportable AE, SAE and unanticipated problems included in the DSMC reports will be submitted to the AAIRB in the PI's Annual Progress Reports.

3.4 POTENTIAL BENEFITS OF THE RESEARCH

Individuals whose data will be included in this research will not receive any direct benefit from their participation in the research study. However, there are several societal benefits to AN people:

1. The primary goal of this research is to understand whether the use of MT-sDNA, as well as high and medium intensity interventions, help increase CRC screening among Alaska Native people. The

- results of this study may be incorporated into Alaska Tribal Health System policies and procedures and lead to more sustainable screening infrastructure and screening services access in the future.
2. This study will also identify barriers to CRC screening experienced by “never” and “rarely screened” Alaska Native people to identify additional strategies to increase screening in these groups, who have among the highest rates of CRC in the world. The benefit of this research is in our improved understanding of screening and access patterns, as well as potential improvements that can be made to the Alaska Tribal Health System to reduce this health disparity.
 3. This research hopes to serve as an example of how to conduct research in a culturally appropriate and respectful manner, and will provide a basis for ongoing discussion around healthcare delivery research among AN people. Translational and healthcare delivery research is proving informative regarding best practices for care, including cancer, in other populations, yet has been underexplored for its potential to be informative regarding cancer prevention and control among AN people. Working closely with tribal stakeholders to develop and conduct this research, we hope to identify strategies and policies that can be implemented in the tribal health system to improve AN healthcare. Our goal is that by working with AN tribal health leaders and community members in this way, this study will join in other current cutting edge science being conducted at the AN Health Campus and pave the way for future research programs that could benefit the health of AN people.

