1. INTRODUCTION

Alaska Native (AN) people have among the highest rates of colorectal cancer (CRC) in the world. Both incidence of and mortality from CRC is **twofold higher among AN people** than US whites; this disparity has persisted for over 40 years.¹ CRC is the second most frequently diagnosed cancer and the second leading cause of cancer-related death for ANs.²

Preventing CRC is an important health priority of AN tribal health leaders and communities. Screening can prevent CRC through the identification and removal of colorectal polyps before they develop into cancer. Screening also allows for the detection and diagnosis of CRC at earlier stages, when treatment has greater likelihood of success with lower impact on quality of life.³⁻⁵

In Alaska, CRC screening, including colonoscopy, is a covered service for AIAN beneficiaries, although screening-related travel is not always covered. Due to the geographic and health care delivery challenges of CRC screening in Alaska, only 59% of AN people have been adequately screened for CRC; and AN screening rates remain persistently lower than national rates.⁶ Efforts to increase CRC screening among AN people have led to some successes, but screening rates still vary substantially by Alaska Tribal health regions, ranging from less than 30% to 73%.⁷

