Although this study will use a cluster-randomized design with the community as the unit of analysis, our research experience in rural Alaska communities indicates minimal within community influence on an individual's personal health decisions. Because an intra-class correlation near zero approaches a simple random sample design, for clarity in our power calculations we have approximated our design as a simple random sample.⁶⁰ The sample size allocation for this study is based on a pre-specified ability to detect an expected difference of 10% or more in screening participation rates for usual care vs any intervention as well as a difference of 10% or more in screening for high intensity vs medium intensity outreach. Given these expected improvements in screening rates, and the expected non-intervention screen rate of 59% based on current rates among AN people, we anticipate more than 80% power to detect a statistically significant difference between screening rates in our medium and high interventions, at alpha of 0.05. To achieve this, we will recruit a sample of 775 or more persons per study arm. An intent-to-screen principle will be used to analyze all eligible patients for the primary outcome: screening participation. All eligible communities will be randomly assigned to an intervention arm at baseline. Group assignment will not be shared because all patients will be randomized at the same time point. Outreach patients will be blinded to the presence of alternate interventions; usual care patients will be blinded to the presence of group assignment altogether.

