We will compare demographic characteristics (sex, age) between those screened using MT-sDNA and colonoscopy, as well as by intervention status (high intensity, medium intensity, usual care) in simple frequency tables. We will use multivariable models to assess the role of intervention status in determining screening rates, adjusting for potential confounders such as age, sex, and other demographic characteristics. Because our primary response is the proportion of persons screened (or the screening rate) we will utilize logistic and/or Poisson regression in our multivariable linear models. For Sub-aim 2.b we will examine how effectiveness of the interventions may vary by sex, age, and rurality using frequency tables and crossing outcome proportions by levels of sex, age, and rurality. Examination of interaction terms (sex by intervention, age by intervention, etc.) in multivariable models, as well as subset analysis as appropriate to illuminate such differences, will allow us to evaluate differences across these covariates in effectiveness of the intervention arms. For Sub-aim 2.c we will obtain an estimate of the sample quality under each of the three intervention conditions and also an estimate of the sample quality likely to result when these interventions are deployed to the larger population and compare those to national sample quality estimates (96%).

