APPENDIX A. POTENTIAL VARIABLES TO BE COLLECTED FROM THE MEDICAL RECORD

1. Contact Information
 - a. Telephone number(s)
 - b. Mailing address
2. Demographics:
 - a. Gender
 - b. Date of birth
 - c. Race(s)
 - d. Hispanic or Latino origin
 - e. Town and state of residence
 - f. County/census area
3. CRC Clinical Data Elements:
 - a. History of CRC screening
 - b. Personal history of CRC or polyps
 - c. Family history of CRC
 - d. Currently experiencing CRC symptoms (rectal bleeding, blood in stool, etc.)
 - e. Test appointment date schedules, or fecal kit distributed
 - f. Screening adherence (test performed, pending, not performed)
 - g. Indication for test(s) (screening, surveillance, diagnostic)
 - h. Type of test(s) performed (colonoscopy, flexible sigmoidoscopy, DCBE, etc.)
 - i. Date of test(s)
 - j. Result of test(s) clinical diagnosis
 - k. Was a biopsy/polypectomy performed
 - l. Was the bowel preparation adequate
 - m. Was the cecum reached during colonoscopy
 - n. Test(s) outcome complete
 - o. Recommended follow-up procedure(s)
 - p. Additional test(s) required? Type
 - q. Histology of the most severe polyp/lesion
 - r. Total number of adenomatous polyp/lesion
 - s. Size of largest adenomatous polyp/lesion
 - t. Histology from surgical resection
 - u. Date surgery performed
 - v. Status of final diagnosis
 - w. Final diagnosis
 - x. Date of final diagnosis
 - y. Recommended next screening/surveillance test
 - z. Indication for next test(s) (screening, surveillance)
 - aa. Recommended time interval till next test
 - bb. Recurrent cancers
 - cc. Status and date of cancer treatment
 - dd. Tumor Registry data: diagnosis, histological type, behavior, primary site, AJCC stage, tumor size, CS-derived SS2000

LITERATURE CITED

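### No community's pre-trial screening rate enters the matching or the model: precision is lost for high v medium, and an existing gap could be read as effect against usual care

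*Combined protocol and SAP*

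**What the plan says.** - **Goal.** Section 3.4 wants to "understand whether the use of MT-sDNA, as well as high and medium intensity interventions, help increase CRC screening among Alaska Native people". Aim 2 (Section 1.1) puts this as a comparison of each intervention with usual care.
- **Allocation.** Sections 2.3 and 3.1 randomise communities between high and medium intensity, and Section 2.3 matches them by size. In both sections usual care is every other community in the region. The Abstract, however, describes a three-arm cluster-randomised trial, and Section 2.5 says all eligible communities are randomly assigned to an intervention arm.
- **Model.** Section 2.5 names the community as the unit of analysis and plans logistic and/or Poisson regression, "adjusting for potential confounders such as age, sex, and other demographic characteristics".
- **Sizing.** Section 2.5 treats the ICC as near zero and uses an "expected non-intervention screen rate of 59% based on current rates among AN people". That figure is the share already adequately screened (Section 1). Section 2.4 excludes people who are up to date, so the 59% is not a pre-trial rate of the trial's outcome.
- **Data.** Section 3.1 uses the records to "identify patients due for screening, provider orders, screening test completion, and pathology results", and Appendix A lists "History of CRC screening". Neither section gives these data a role in matching or adjustment.

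**The concern.** A community's recent screening rate reflects colonoscopy access, travel and clinic practice, which age, sex and community size describe poorly. It is a natural predictor of the same community's rate in the trial year. Individual screening history is not the same thing: everyone analysed is overdue by design, and people screened in the previous year have left the list.

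Two things are at stake.

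- **High v medium.** With perhaps six communities per arm, chance differences in underlying rates stay in the estimate, and between-community variance that could be explained stays in the error term.
- **Usual care.** If the reference group is whatever communities remain, randomisation does not balance it against the outreach groups. A 5-point gap that was there before the trial, if nothing removed it, would equal half the 10-point target.

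**Working it through.** **Inputs from the plan.** 775 per arm, two-sided 0.05 (the sidedness is assumed), and a 10-point difference, giving 59% v 69% and 69% v 79% (Section 2.5; Sub-aim 2.a adds 10 and 20 points to usual care). The number of communities per arm, k, is unsettled: at least six per arm in Sub-aim 2.a, but both twelve communities and 16 per intervention in Section 2.3. Both k = 6 and k = 16 are run.

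**Assumptions, because the documents give no values.** ICC from 0 to 0.03. True-rate correlation r of 0.5, 0.7 or 0.8 between a community's pre-trial and trial-year rates. Equal community sizes, a baseline year as large as the trial year, and no allowance for size matching.

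**The plan's own figure.** With no clustering, the standard error (SE) for 59% v 69% is √[(0.2419 + 0.2139)/775] = 2.43 points, and power is about 98%. For 69% v 79% power is above 99%. The stated "we anticipate more than 80% power to detect a statistically significant difference" therefore holds, with room to spare, but only at ICC zero.

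**High v medium without a baseline rate.** With m = 775/k,

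SE² = [p₁(1−p₁) + p₂(1−p₂)] × [ICC + (1−ICC)/m] / k.

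For k = 6, m = 129.2, ICC 0.02: 0.3798 × [0.02 + 0.00759]/6 = 0.001746, so SE = 4.18 points. Power from the noncentral t with 10 df is 58%.

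**With the baseline rate as covariate.** One year's observed rate is a noisy measure of the true rate. Its reliability is ICC/[ICC + (1−ICC)/m] = 0.02/0.02759 = 0.725. ICC in the formula becomes ICC × (1 − r² × reliability), with one df fewer. At r = 0.7: 0.3798 × [0.02 × (1 − 0.49 × 0.725) + 0.00759]/6 = 0.001297, so SE = 3.60 points and power is 70%.

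| k per arm, ICC | Reliability | Power without | Power with, r = 0.5 / 0.7 / 0.8 |
|---|---|---|---|
| 6, zero | – | 98.2% | 97.9% at any r |
| 6, 0.01 | 0.57 | 77% | 79 / 82 / 85% |
| 6, 0.02 | 0.72 | 58% | 63 / 70 / 74% |
| 16, 0.03 | 0.60 | 80% | 84 / 87 / 89% |

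Setting reliability to 1 gives 65/76/83% in the third row and 86/92/95% in the fourth. Those figures require a baseline rate measured without error.

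**Chance imbalance between two arms of six.** The between-community SD is √(ICC × 0.59 × 0.41), which is 4.9 points at ICC 0.01 and 7.0 at 0.02. Multiplying by √(2/6) gives an SD of the arm difference of 2.8 and 4.0 points. The chance of a gap above 5 points is 8% and 21%.

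**Change score or covariate, usual care v medium (59% v 69%).** Take k = 6 in both groups and a baseline of 59%. With v_f and v_b the values of p(1−p) at follow-up and baseline, the change-score variance per group is {ICC × [v_f + v_b − 2r√(v_f v_b)] + (1−ICC)(v_f + v_b)/m}/k.

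| ICC | SE, follow-up only | SE, change score, r = 0.5 / 0.7 / 0.8 | SE, covariate, r = 0.5 / 0.7 / 0.8 |
|---|---|---|---|
| 0.01 | 3.7 | 4.5 / 4.1 / 3.9 | 3.5 / 3.4 / 3.3 |
| 0.02 | 4.6 | 5.2 / 4.6 / 4.3 | 4.3 / 3.9 / 3.7 |

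At ICC 0.01 the change score is worse than ignoring the baseline at every r. At ICC 0.02 it is clearly better only at r = 0.8. The covariate lowers the SE in every cell.

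**The case against.** **The goal does not require change from baseline.** A reader might infer from the word increase that follow-up rates alone cannot answer the question. The documents do not support that: the hypothesis is a between-arm contrast, and Section 3.4 lists societal benefits rather than defining an estimand. This part of the objection stands in full.

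**High v medium is randomised.** A reader might infer bias. There is none: prior differences between these arms are chance, and a proper cluster-level error already reflects them. The low power at ICC 0.02 comes from sizing the trial without clustering, which adjustment only mitigates.

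**The ICC may be near zero, and r may be low.** Section 2.5 bases its near-zero ICC on experience and gives no estimate, while Aim 1 (Section 1.1) anticipates variation in adherence between communities. Section 1 reports rates from under 30% to 73%, but these are between regions and say little about communities within the one or two regions used. Pre-trial screening was probably mostly colonoscopy, and a mailed kit aims to bypass the barriers to colonoscopy, so r could fall below the range shown. The gain is therefore uncertain, but if it is absent the loss is one degree of freedom.

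**The covariate list is open, and screening history is collected.** Section 2.5 does say such as, and time since last screening could usefully separate never-screened from lapsed patients. But the class it names is demographic, and an open list is not prespecification.

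**Conclusion.** The point holds as an omission worth correcting. Matching on size and adjustment for demographics leave a community's earlier rate of the outcome unused.

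- **High v medium.** This is a matter of precision and chance imbalance. Under the stated assumptions the gain is about 5 to 16 percentage points of power with six communities per arm at ICC 0.02, and about 4 to 9 with 16 per arm at ICC 0.03. It vanishes at ICC zero. All these figures start from 59%, which is not the 12-month completion rate among overdue people, so they show scale only.
- **Usual care.** The risk of reading an existing gap as effect is conditional on usual care being the remaining communities, as Sections 2.3 and 3.1 say and Section 2.5 leaves unclear. Size matching and age and sex adjustment may remove only part of such a gap. A reader might infer that these contrasts are known to be biased. The documents show no gap between communities, and the 5 points is an illustration.

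Adjustment would reduce the problem for usual care but would not make a non-randomised comparison randomised, because a baseline rate measured with noise under-corrects.

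**What to change.** 1. In Section 2.5, prespecify each community's screening completion rate in the 12 months before randomisation, among 45-75-year-olds who were overdue at the start of that period. Use the same codes and the same calendar months in every community, including usual care.
2. Enter it as a community-level covariate in a cluster-level or cluster-adjusted model for all contrasts.
3. Do not make a change score primary. It can increase the SE and rests on parallel trends. It may be shown as a sensitivity analysis.
4. Reconcile Sections 2.3, 3.1 and 2.5 on whether usual-care communities are randomised, and settle the number of communities per arm.

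**Cost.** One degree of freedom, SAP wording and an aggregate count from the records. The count is more than a by-product of the existing query: eligibership under Section 2.4 must be reconstructed one year earlier, including people since screened who are no longer on the list. Section 3.5 calls for an IRB modification if analyses are added. The baseline year may overlap COVID-19 disruption, which could lower the correlation; shared calendar months help only so far as the disruption was similar across communities. The wording should be fixed before outcome data are reviewed.
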